13.6. Immunogenicity

A validated immunoassay will be used to assay samples for the presence of, and measure titers of, anti-BIIB092 antibodies in serum. Samples will be collected on Study Day 1 and at Weeks 4,

24, 48, 76, 80, 104, 116, 156, 176, 196, 224, and 238/FUV (see Section 5). All samples will be collected predose.

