2.3 Study Design

This is a Phase 2, randomized, double-blind, placebo-controlled, parallel-group study consisting of a double-blind, placebo-controlled period and an LTE period.

The study includes 2 substudies to address exploratory study objectives: a tau PET substudy and a CSF sampling substudy. The tau PET substudy is mandatory at study sites that have access to the ¹⁸F-MK6240 PET radioligand and have the capability to perform ¹⁸F-MK6240 PET scans. During the placebo-controlled period, the CSF sampling substudy is mandatory at all study sites that do not have access to the ¹⁸F-MK6240 PET radioligand. Participants will provide consent during Screening to participate in at least 1 of these substudies during the placebo-controlled period. Participants enrolled in the LTE period and who are participating in the tau PET substudy are required to continue participation in the tau PET substudy. Participation in the CSF sampling substudy during the LTE will be optional for all study participants, although participation is encouraged.

This study will be conducted in participants aged 50 to 80 years, inclusive, with MCI due to AD or mild AD according to National Institute on Aging-Alzheimer's Association criteria. Participants must have amyloid beta positivity confirmed at Screening by either CSF sampling or an amyloid PET scan. Participants must also perform at least 1 standard deviation below the age-adjusted normative mean on either the ISLT or the International Shopping List Test Delayed Recall and have a CDR global score of 0.5 for MCI due to AD or 0.5 or 1 for mild AD, an MMSE score of 22 to 30 (inclusive), and a CDR Memory Box score of ≥ 0.5 .

During the dose-blinded LTE period, participants will receive BIIB092 by IV once every 4 weeks beginning at Week 80. Participants who were randomized to receive BIIB092 during the placebo-controlled period will continue to receive BIIB092 at the dose they were randomly assigned. Participants randomized to receive placebo during the placebo-controlled period will receive BIIB092 at the high dose (2000 mg) once every 4 weeks during the LTE period.

The total duration for participants who complete the placebo-controlled period and do not enter the LTE period will be approximately 99 weeks. For participants who complete both the placebo-controlled period and the LTE period, the total study duration will be approximately 247 weeks.

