3.2 Analyses Period

Depending on the purpose, different analyses will be conducted on the following study periods:

1. LTE period. Only data in the LTE period will be included in these analyses. This LTE analysis period will be applied to all the AE analyses, and the analyses will include all subjects who were dosed in the LTE period.
2. Placebo-controlled and LTE period. All the data in the placebo-controlled and LTE periods will be included in these analyses. This analysis period will be applied to analyses including, but not limited to all efficacy analyses and listings. The analyses will include all subjects who were dosed in the study including those who did not enroll into the LTE period. For example, line plot of CDR sum of box mean change from baseline over time. in the placebo-controlled and LTE period.
3. Placebo-controlled and LTE active treatment period. Active treatment period is defined as the study period(s) that a subject received BIIB092. For early start subjects – subjects who received BIIB092 in both placebo-controlled and LTE period, all the data (placebo-controlled and LTE periods) will be included in the analyses. For late start subjects – subjects who received placebo in the Placebo-controlled period and BIIB092 in the LTE period, only data in the LTE period will be included. This analysis period will be applied to majority of safety tables, and the analyses will include all subjects who were dosed in the study except for subjects who received only placebo in the placebo-controlled period and did not get dosed in the LTE period. An example is the incidence rate of adverse events in the placebo-controlled and LTE active treatment period.

Subjects to be included in a certain output is determined by both the analysis set and the analysis period. For example, the incidence table of adverse events in the LTE period will include subjects in the safety population for the LTE period, i.e., all randomized subjects who received at least one dose of study treatment in the LTE period. The incidence rate table of adverse events in the placebo-controlled and LTE active treatment period will include subjects in the safety population for the active treatment period, i.e., all randomized subjects who received at least one dose of study treatment in the active treatment period. In this SAP we do not separately define the analysis set in each analysis period.

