5.4.5 ECG Data

5.4.5.1 ECG analyses

Actual values of numeric ECG parameters will be summarized by visit. number of evaluable subjects, mean, standard deviation, 25% and 75% quartiles, min and max values will be presented at each visit for placebo-controlled and LTE period active treatment period. Similarly change from baseline values will be summarized in the same fashion for placebo-controlled and LTE active treatment period.

Summary of ECGs (number of normal, <abnormal, not adverse event>, or <abnormal, adverse event>) at scheduled visits will be presented by the LTE treatment group through the placebo-controlled and LTE active treatment period.

CONFIDENTIAL

The information contained herein may not be used, disclosed, or published without the written consent of Biogen MA Inc.

	Statistical Analysis Plan Long-Term Extension Period	V1.0
---	---	-------------

Shift table from normal or unknown ECG at baseline to ever abnormal ((<abnormal, not adverse event>, or <abnormal, adverse event>) post-baseline ECG will be summarized for the placebo-controlled and LTE active treatment group. The worst post-baseline record of each subject is selected.

For the above mentioned ECG analyses, for early start subjects, the placebo-controlled baseline will be used while for late start subjects, the LTE baseline will be used.

In addition, PR and QTcF values will be summarized. Please see the detail in the SAP for placebo-controlled period.

Visit windows for by visit summaries

For ECG data that are summarized by visit, assessment from all scheduled visits, EOT visit, EOS visit and unscheduled visits will be mapped to an appropriate analysis visit using a windowing scheme ([Appendix I](#)).

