5.7 Anti-Drug Antibody Analysis

5.7.1 Analysis Methods for Anti-Drug Antibody Data

Anti-Drug Antibody (ADA) population will be used to analyze ADA data.

The baseline value is defined as the last available value prior to first dose of placebo or BIIB092 in placebo-controlled period. For subjects with missing baseline assessment, the most conservative approach will be taken and they will be considered negative for ADA at baseline.

For the definitions of treatment emergent positive, persistently positive, and transiently positive, please refer to the placebo-controlled SAP.

Summary table listing the number and percentage of all anti-BIIB092-positive and -negative antibody events by LTE treatment group and visits throughout the placebo-controlled and LTE active treatment period will be displayed.

In addition, a summary table of patients with treatment-emergent, persistent, and transient responses will be presented by LTE treatment group during the placebo-controlled and LTE active treatment period. A listing of anti-BIIB092 antibody results will also be provided.

Visit windows for by visit summaries

For ADA data that are summarized by visit, assessment from all scheduled visits, EOT visit, and unscheduled visits will be mapped to an appropriate analysis visit using a windowing scheme ([Appendix I](#)).

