Baseline	1	Most recent non-missing value prior to the first infusion in LTE	
Week 24	169	[2, 253]	Week 100
Week 48	337	[254, 421]	Week 124
Week 72	505	[422, 526]	Week 148
Week 100	701	[527, 785]	Week 172
Week 124	869	[786, 953]	Week 196
Week 148	1037	[954, 1121]	Week 220 and Week 226
Week 172	1205	≥1122	Week 238

Note: Study day and analysis visit window are derived based on the first day of study drug in LTE.

Table 4. Visit Window for Coagulation Panel by Visit Summaries using Placebo-Controlled Baseline

Analysis visit	Target visit day	Analysis visit window
Baseline	1	Most recent non-missing pre-dose value
Week 8	57	[2, 183]
Week 44	309	[184, 407]
Week 72	505	[408, the end day of the placebo-controlled period ¹]
Week 124	869	[the start day of the LTE period ² , 1037]
Week 172	1205	[1038, 1373]
Week 220	1541	> 1373

CONFIDENTIAL

The information contained herein may not be used, disclosed, or published without the written consent of Biogen MA Inc.

1 The end day of the placebo-controlled period is the last day before the first infusion in LTE for subjects who enter LTE and is the last day in study for subjects who do not enter LTE.
2 The start day of the LTE period is the day of the first infusion in the LTE period.

Table 5. Visit Window for Coagulation Panel by Visit Summaries using LTE Baseline

Analysis visit	Target visit day	Analysis visit window	Protocol visit
Baseline	Most recent non-missing value	Most recent non-missing value prior to the first infusion in LTE	Week 72
Week 44	309	[2, 477]	Week 124
Week 72	645	[478, 813]	Week 172
Week 124	981	> 813	Week 220

Table 6. Visit Windows for ECG by Visit Summaries for Placebo-Controlled and LTE Period using Placebo-Controlled Baseline

Analysis visit	Target visit day	Analysis visit window
Baseline	1	Most recent non-missing pre-dose value
D1 Post dose	1	Day1: 15 min post dose or 1 hour post dose
Week 12	85	[2, 127]
Week 24	169	[128, 253]
Week 48	337	[254, 421]
Week 72	505	[422, 526]
Week 78	547	[527, 630* or the end day of the placebo-controlled period ¹]
Week 90*	631	[631, the last day in the study]
Week 104	729	[the start day of the LTE period ² , 813]
Week 128	897	[814, 981]
Week 152	1065	[982, 1149]
Week 176	1233	[1150, 1317]
Week 200	1401	[1318, 1492]
Week 226	1582	[1493, 1625]
Week 238	1667	[1626, the end day of the LTE period]

* Applicable only for the subjects who do not go to LTE. They are expected to have week 90 follow-up assessment.

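### 'Ever' ECG and ADA counts are not comparable between early- and late-start 2000 mg, because late start has no scheduled on-drug ECG or ADA sample before Week 24 on BIIB092

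*SAP*

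**What the plan says.** **First exposure.** SAP 2.3 says that in the LTE "participants will receive BIIB092 by IV once every 4 weeks beginning at Week 80". For those who had placebo beforehand, this is their first BIIB092. SAP 3.2 builds the active treatment period accordingly: for subjects on placebo and then "BIIB092 in the LTE period, only data in the LTE period will be included". Early-start subjects contribute both periods.

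**ADA.** Protocol 13.6 gives one schedule: "Samples will be collected on Study Day 1 and at Weeks 4", then "24, 48, 76, 80, 104, 116, 156, 176, 196, 224, and 238/FUV", with every sample taken before dosing. SAP 5.7.1 then plans that "a summary table of patients with treatment-emergent, persistent, and transient responses will be presented by LTE treatment group" over the active treatment period. The definitions of those response types are left to the placebo-controlled SAP.

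**ECG.** SAP Appendix I, Table 6 lists a Day 1 post-dose analysis visit, "Day1: 15 min post dose or 1 hour post dose", then Weeks 12, 24, 48, 72 and 78. Protocol Table 2 has no ECG at Week 80 and marks ECGs only at Weeks 104 and 128. SAP Table 7 (LTE baseline) has no Day 1 post-dose row and starts at target day 169. SAP 5.4.5.1 plans a "Shift table from normal or unknown ECG at baseline to ever abnormal", keeping each subject's worst post-baseline record.

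**Adjustment.** SAP 5.4.2.2 allows for unequal follow-up, optionally, for AE rates only. Nothing comparable is stated for ADA or ECG.

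**The concern.** A count of subjects who ever had a finding depends on how often and when they were tested. The placebo-controlled schedule looks closely at first exposure. The LTE schedule, which is first exposure for the late-start group, does not do so for ECG or ADA. Adjusting for person-time would not repair this, because the number of looks per unit of time differs.

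The two 2000 mg columns will stand side by side in these tables. SAP 5.4.2.1 already contrasts the same two groups in one AE table, so a reader will naturally do the same here. A lower late-start figure could then be taken as an effect of starting later or of shorter exposure, when part of it comes from the visit schedule. Protocol Table 2 does repeat the standing blood pressure checks at Weeks 80 to 92, so a first-exposure schedule was restored for that measure.

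**Working it through.** **Step 1: reproduce the SAP's own day.** Protocol study day = 7 × week + 1, so Week 80 is day 561 and Week 104 is day 729. LTE day = 729 − 561 + 1 = 169. This matches the first post-baseline target day in SAP Table 7 (ECG) and Table 11 (ADA), and (169 − 1)/7 = 24 weeks on drug. The Week 80 ADA sample is predose, so it is not an on-drug look.

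**Step 2: put both groups on time since first BIIB092.** For late start, on-drug week = study week − 80.

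| | Early start | Late start |
|---|---|---|
| ECG | Day 1 post-dose, 12, 24, 48, 72, 78 | 24, 48, 72 (Weeks 104, 128, 152) |
| ADA | 4, 24, 48, 76 | 24, 36, 76 (Weeks 104, 116, 156) |

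**Step 3: count scheduled looks, early versus late.**

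| On-drug time | ECG | ADA |
|---|---|---|
| Before Week 24 | 2 vs 0 | 1 vs 0 |
| Through Week 24 | 3 vs 1 | 2 vs 1 |
| Through Week 48 | 4 vs 2 | 3 vs 2 |
| Through Week 76 | 5 vs 3 | 4 vs 3 |
| Through Week 78 | 6 vs 3 | 4 vs 3 |

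**Step 4: illustrate the size.** Assume the same probability p of a finding at each look in both groups, with looks independent. The documents give no p, so a range is shown. P(ever) = 1 − (1 − p)^k for k looks.

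| p | ECG through Week 78 (k = 6 vs 3) | ADA through Week 76 (k = 4 vs 3) |
|---|---|---|
| 1% | 5.9% vs 3.0% | 3.9% vs 3.0% |
| 5% | 26.5% vs 14.3% | 18.5% vs 14.3% |
| 10% | 46.9% vs 27.1% | 34.4% vs 27.1% |

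At p = 5%: 1 − 0.95^6 = 0.265, 1 − 0.95^4 = 0.185 and 1 − 0.95^3 = 0.143. The ratios are about 1.9 for ECG and 1.3 for ADA. Through Week 24 only, p = 5% gives ECG 14.3% vs 5.0% and ADA 9.75% vs 5.0%.

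**Step 5: transient ADA.** Suppose a response lasts between 4 and 12 weeks (uniform, mean 8) and is detected if a scheduled sample falls inside it.
- Onset uniform over on-drug Weeks 0–12: the early-start Week 4 sample catches every onset by Week 4, so 4/12 = 33%. Late start catches none before its Week 24 sample, so 0%.
- Onset uniform over Weeks 24–36: the late-start Week 36 sample catches 8/12 = about 67%. Early start has nothing between Weeks 24 and 48, so 0%.

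The direction reverses with onset time.

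**Step 6: other measures.** Hematology and chemistry start at Week 12 for early start (SAP Table 2) and at Week 100 for late start (Protocol Table 2), which is on-drug Week 20. Coagulation is first at Week 8 (SAP Table 4) against LTE day 309 (SAP Table 5), and (309 − 1)/7 = on-drug Week 44. The later start is therefore not confined to ADA and ECG.

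**The case against.** The strongest reply is that these are descriptive tables: the SAP plans no early-versus-late test for ADA or ECG, and the LTE ADA endpoint is exploratory. That stands. It limits the weight of the point but does not make the columns comparable.

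Second, the by-visit outputs already hold much of the matched data. ECG values and status, and ADA positives, are tabulated by visit, and SAP Table 7 targets days 169, 337 and 505, which are on-drug Weeks 24, 48 and 72. This also stands, but by-visit rows do not give a per-subject 'ever' count on matched looks. For ADA, Table 11 labels protocol Week 116 as its Week 48 visit, although that sample falls on LTE day 253 (36 weeks on drug), inside the Week 24 window.

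Third, the 24-week gap is not universal. A late-start participant whose last dose is at Week 80, 84 or 88 has the 14-week follow-up visit, with ADA and ECG, at Week 94, 98 or 102. An early termination visit carries an ECG, and unscheduled assessments can occur.

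Fourth, later late-start looks may be sparse. SAP 5.2.4 stops its infusion categories at 26, against 20 placebo-controlled infusions, and SAP 5.6.2 says nobody reached Week 226. Short LTE exposure is an inference from these, but it is a reason to build the fix around Week 24.

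A reader might go further and infer that late start must show fewer transient ADA responses. Step 5 does not support that, and the response definitions are in a SAP not available here. A reader might also count ADA through Week 80 and obtain 5 versus 3. That counts early-start samples four weeks apart as separate looks and depends on the cut-off; through Week 96 it is 5 versus 4.

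**Conclusion.** The point holds, as one of comparability in descriptive tables. For participants who stay on treatment, the unrestricted 'ever abnormal' ECG shift and the subject-level ADA response table cannot be compared between early- and late-start 2000 mg, even at equal time on drug. The ECG imbalance is the material one, at 6 versus 3 looks through Week 78. The ADA imbalance is one sample through Week 76, with no fixed direction for transient responses.

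The look counts follow directly from the schedules. The percentages rest on an assumed equal and independent per-look probability. Standing ECG abnormalities and persistent antibodies are correlated between looks, which would shrink the gaps. A reader might infer that late-start safety findings in general are understated. The documents do not support that: AEs are recorded continuously throughout the LTE, independently of ECG and ADA visits.

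**What to change.** In SAP 5.4.5.1 and 5.7.1, for the early- and late-start high-dose groups:

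- Add an 'ever' summary restricted to looks both groups have at matched time on BIIB092. Use Week 24 at minimum; add ECG Weeks 48 and 72 and ADA Week 76 only where late-start data exist.
- Show the number of evaluable looks per subject beside the unrestricted counts.
- Report the Day 1 post-dose and Week 12 ECG results and the Week 4 ADA results as early-start only.
- Footnote that the unrestricted 'ever' figures are not comparable between early and late start, because late start had no scheduled on-treatment ECG or ADA sample before 24 weeks on drug.

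The cost is one restricted table each for ECG and ADA, with no new samples or visits. The downside is that the restricted tables use fewer early-start results, which is why the unrestricted counts should stay alongside them.

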5.8 Additional Exploratory Endpoints

5.8.1 Health Outcomes

The FAS will be used for the analysis of health outcomes data for LTE period. The result will be listed by LTE treatment group for placebo-controlled and LTE period.

CONFIDENTIAL

The information contained herein may not be used, disclosed, or published without the written consent of Biogen MA Inc.

6 Appendix I: Visit Window Mapping

For data that are summarized by visit and longitudinal analysis, assessment from all scheduled visits including EOT visit and EOS visit, and all unscheduled visits will be mapped to an appropriate analysis visit using a windowing scheme. Analysis visit windows are defined in [Table 1 - Table 12] for different endpoints.

If there are 2 or more assessments from visits other than EOT or EOS visits mapped to the same analysis visit for a subject, the assessment that is closest to the target visit day will be used for analysis. If there are 2 or more assessments from visits other than EOT or EOS visits mapped to the same analysis visit with the same distance from the target visit day, then select the later one(s) for the analysis. If there are 2 or more assessments from visits other than EOT or EOS visits mapped to the same analysis visit and on the same day, use the average value for quantitative parameters and the worst value for qualitative parameters for analysis.

Table 1. Visit Windows for Efficacy Endpoints

Efficacy Endpoint	Analysis visit	Target visit day	Analysis visit window
CDR, NPI-10, ADAS-Cog13, FAQ, and ADCS-ADL	Baseline	1	Most recent non-missing pre-dose value
	Week 24	169	[2, 267]
	Week 52	365	[268, 456]
	Week 78	547	[457, the end day of the placebo-controlled period ¹]
	Week 104	729	[one day after the start day of the LTE period ² , 813]
	Week 128	897	[814, 981]
	Week 152	1065	[982, 1149]
	Week 176	1233	[1150, 1317]
	Week 200	1401	[1318, 1492]
	Week 226	1582	≥1493
ISLT, DKEFS, DSST, Trails A,	Baseline800-	1	Most recent non-missing pre-dose value
	Week 12	85	[2, 141]
	Week 28	197	[142, 239]
	Week 40	281	[240, 337]
	Week 56	393	[338, 435]
	Week 68	477	[436, 512]
	Week 78	547	[513, the end day of the placebo-controlled period ¹]
	Week 108	757	[one day after the start day of the LTE period ² , 841]

CONFIDENTIAL

The information contained herein may not be used, disclosed, or published without the written consent of Biogen MA Inc.

Efficacy Endpoint	Analysis visit	Target visit day	Analysis visit window
	Week 132	925	[842, 1009]
	Week 156	1093	[1010, 1261]
	Week 204	1429	[1262, 1506]
	Week 226	1582	≥1507
eCog	Baseline	1	Most recent non-missing pre-dose value
	Week 28	197	[2, 295]
	Week 56	393	[296, 470]
	Week 78	547	[471, the end day of the placebo-controlled period ¹]
	Week 108	757	[one day after the start day of the LTE period ² , 841]
	Week 132	925	[842, 1009]
	Week 156	1093	[1010, 1261]
	Week 204	1429	[1262, 1506]
	Week 226	1582	≥1507
MMSE	Baseline	1	Most recent non-missing pre-dose value
	Week 12	85	[2, 127]
	Week 24	169	[128, 225]
	Week 40	281	[226, 323]
	Week 52	365	[324, 421]
	Week 68	477	[422, 512]
	Week 78	547	[513, the end day of the placebo-controlled period ¹]
	Week 104	729	[one day after the start day of the LTE period ² , 813]
	Week 128	897	[814, 981]
	Week 152	1065	[982, 1149]
	Week 176	1233	[1150, 1317]
	Week 200	1401	[1318, 1492]
	Week 226	1582	≥1493

1 The end day of the placebo-controlled period is the last day on or before the first infusion in LTE for subjects who enter LTE and is the last day in study for subjects who do not enter LTE. 2 The start day of the LTE period is the day of the first infusion in the LTE period.
			

CONFIDENTIAL

The information contained herein may not be used, disclosed, or published without the written consent of Biogen MA Inc.

Table 2. Visit Windows for Laboratory by Visit Summaries using Placebo-Controlled Baseline

Analysis visit	Target visit day	Analysis visit window
Baseline	1	Most recent non-missing pre-dose value
Week 12	85	[2, 127]
Week 24	169	[128, 253]
Week 48	337	[254, 421]
Week 72	505	[422, 526]
Week 78	547	[527, 630* or the end day of the placebo-controlled period ¹]
Week 90*	631	[631, the last day in the study]
Week 100	701	[the start day of the LTE period ² , 785]
Week 124	869	[786, 953]
Week 148	1037	[954, 1121]
Week 172	1205	[1122, 1289]
Week 196	1373	[1290, 1457]
Week 220	1541	[1458, 1562]
Week 226	1582	[1563, 1625]
Week 238	1667	≥1626

* Applicable only for the subjects who do not go to LTE. They are expected to have week 90 follow-up assessment.
 1 The end day of the placebo-controlled period is the last day before the first infusion in LTE for subjects who enter LTE and is the last day in study for subjects who do not enter LTE.
 2 The start day of the LTE period is the day of the first infusion in the LTE period.

Table 3. Visit Windows for Laboratory by Visit Summaries using LTE Baseline

Analysis visit	Target visit day	Analysis visit window	Protocol visit
Baseline	1	Most recent non-missing value prior to the first infusion in LTE	
Week 24	169	[2, 253]	Week 100
Week 48	337	[254, 421]	Week 124
Week 72	505	[422, 526]	Week 148
Week 100	701	[527, 785]	Week 172
Week 124	869	[786, 953]	Week 196
Week 148	1037	[954, 1121]	Week 220 and Week 226
Week 172	1205	≥1122	Week 238

Note: Study day and analysis visit window are derived based on the first day of study drug in LTE.

Table 4. Visit Window for Coagulation Panel by Visit Summaries using Placebo-Controlled Baseline

Analysis visit	Target visit day	Analysis visit window
Baseline	1	Most recent non-missing pre-dose value
Week 8	57	[2, 183]
Week 44	309	[184, 407]
Week 72	505	[408, the end day of the placebo-controlled period ¹]
Week 124	869	[the start day of the LTE period ² , 1037]
Week 172	1205	[1038, 1373]
Week 220	1541	> 1373

CONFIDENTIAL

The information contained herein may not be used, disclosed, or published without the written consent of Biogen MA Inc.

1 The end day of the placebo-controlled period is the last day before the first infusion in LTE for subjects who enter LTE and is the last day in study for subjects who do not enter LTE.
2 The start day of the LTE period is the day of the first infusion in the LTE period.

Table 5. Visit Window for Coagulation Panel by Visit Summaries using LTE Baseline

Analysis visit	Target visit day	Analysis visit window	Protocol visit
Baseline	Most recent non-missing value	Most recent non-missing value prior to the first infusion in LTE	Week 72
Week 44	309	[2, 477]	Week 124
Week 72	645	[478, 813]	Week 172
Week 124	981	> 813	Week 220

Table 6. Visit Windows for ECG by Visit Summaries for Placebo-Controlled and LTE Period using Placebo-Controlled Baseline

Analysis visit	Target visit day	Analysis visit window
Baseline	1	Most recent non-missing pre-dose value
D1 Post dose	1	Day1: 15 min post dose or 1 hour post dose
Week 12	85	[2, 127]
Week 24	169	[128, 253]
Week 48	337	[254, 421]
Week 72	505	[422, 526]
Week 78	547	[527, 630* or the end day of the placebo-controlled period ¹]
Week 90*	631	[631, the last day in the study]
Week 104	729	[the start day of the LTE period ² , 813]
Week 128	897	[814, 981]
Week 152	1065	[982, 1149]
Week 176	1233	[1150, 1317]
Week 200	1401	[1318, 1492]
Week 226	1582	[1493, 1625]
Week 238	1667	[1626, the end day of the LTE period]

* Applicable only for the subjects who do not go to LTE. They are expected to have week 90 follow-up assessment.
1 The end day of the placebo-controlled period is the last day before the first infusion in LTE for subjects who enter LTE and is the last day in study for subjects who do not enter LTE.
2 The start day of the LTE period is the day of the first infusion in the LTE period.

Table 7. Visit Windows for ECG by Visit Summaries using LTE Baseline

Analysis visit	Target visit day	Analysis visit window	Protocol visit
Baseline	Most recent non-missing value prior to the first infusion in LTE	Most recent non-missing value prior to the first infusion in LTE	Week 78

CONFIDENTIAL

The information contained herein may not be used, disclosed, or published without the written consent of Biogen MA Inc.

Analysis visit	Target visit	visit	Analysis visit window	Protocol visit
Week 24	169		[the start day of the LTE period, 253]	Week 104
Week 48	337		[254, 421]	Week 128
Week 72	505		[422, 589]	Week 152
Week 104	673		[590, 757]	Week 176
Week 128	841		[758, 932]	Week 200
Week 152	1023		[933, 1065]	Week 226
Week 176	1107		>1065	Week 238

Day 1 is the first infusion day in LTE period

Table 8. Visit Windows for Vital Sign by Visit Summaries using Placebo-Controlled Baseline

Analysis visit	Target visit day	Analysis visit window
Baseline	1	Most recent non-missing pre-dose value
D1 Post dose	1	Day 1 post dose infusion (if more than one Day 1 post dose results available, the average of the available results will be used)
Week 4– Pre dose	29	[2, 43] (Pre-dose assessment)
Week 4- Post dose	29	[2, 43] (Post dose assessment)
Week 8– Pre dose	57	[44, 71] (Pre-dose assessment)
Week 8- Post dose	57	[44, 71] (Post dose assessment)
Week 12– Pre dose	85	[72, 99] (Pre-dose assessment)
Week 12- Post dose	85	[72, 99] (Post dose assessment)
Week 16	113	[100, 127]
Week 20	141	[128, 155]
Week 24	169	[156, 183]
Week 28	197	[184, 211]
Week 32	225	[212, 239]
Week 36	253	[240, 267]
Week 40	281	[268, 295]
Week 44	309	[296, 323]
Week 48	337	[324, 351]
Week 52	365	[352, 379]
Week 56	393	[380, 407]
Week 60	421	[408, 435]
Week 64	449	[436, 463]
Week 68	477	[464, 491]
Week 72	505	[492, 519]
Week 76	533	[520, 540]
Week 78	547	[541, 589* or the end day of the placebo-controlled period ¹]
Week 90*	631	[590, the last day in the study]
Week 80	561	[the start day of the LTE period ² , 575]
Week 84	589	[576, 603]
Week 88	617	[604, 631]
Week 92	645	[632, 659]
Week 96	673	[660, 687]

CONFIDENTIAL

The information contained herein may not be used, disclosed, or published without the written consent of Biogen MA Inc.

Analysis visit	Target visit day	Analysis visit window
Week 100	701	[688, 715]
Week 104	729	[716, 743]
Week 108	757	[744, 771]
Week 112	785	[772, 799]
Week 116	813	[800, 827]
Week 120	841	[828, 855]
Week 124	869	[856, 883]
Week 128	897	[884, 911]
Week 132	925	[912, 939]
Week 136	953	[940, 967]
Week 140	981	[968, 995]
Week 144	1009	[996, 1023]
Week 148	1037	[1024, 1051]
Week 152	1065	[1052, 1079]
Week 156	1093	[1080, 1107]
Week 160	1121	[1108, 1135]
Week 164	1149	[1136, 1163]
Week 168	1177	[1164, 1191]
Week 172	1205	[1192, 1219]
Week 176	1233	[1220, 1247]
Week 180	1261	[1248, 1275]
Week 184	1289	[1276, 1303]
Week 188	1317	[1304, 1331]
Week 192	1345	[1332, 1359]
Week 196	1373	[1360, 1387]
Week 200	1401	[1388, 1415]
Week 204	1429	[1416, 1443]
Week 208	1457	[1444, 1471]
Week 212	1485	[1472, 1499]
Week 216	1513	[1500, 1527]
Week 220	1541	[1528, 1555]
Week 224	1569	[1556, 1576]
Week 226	1582	[1577, 1625]
Week 238	1667	[1626, the end of the LTE period]

* Applicable only for the subjects who do not go to LTE. They are expected to have week 90 follow-up assessment.

1 The end day of the placebo-controlled period is the last day before the first infusion in LTE for subjects who enter LTE, and is the last day in study for subjects who do not enter LTE.

2 The start day of the LTE period is the day of the first infusion in the LTE period.

Table 9. Visit Windows for Vital Sign by Visit Summaries using LTE baseline

CONFIDENTIAL

The information contained herein may not be used, disclosed, or published without the written consent of Biogen MA Inc.

Statistical Analysis Plan
Long-Term Extension Period

V1.0

Analysis visit	Target visit day	Analysis visit window	Protocol visit
LTE Baseline	1	Most recent non-missing value prior to the first infusion in LTE	Week 80 pre dose
D1 Post dose	1	Day 1 post dose infusion (if more than one Day 1 post dose results available, the average of the available results will be used)	Week 80 post dose
Week 4- Pre dose	29	[2, 43] (Pre-dose assessment)	Week 84 (Pre-dose assessment)
Week 4-- Post dose	29	[2, 43] (Post dose assessment)	Week 84 (Post dose assessment)
Week 8- Pre dose	57	[44, 71] (Pre-dose assessment)	Week 88 (Pre-dose assessment)
Week 8- Post dose	57	[44, 71] (Post dose assessment)	Week 88 (Post dose assessment)
Week 12- Pre dose	85	[72, 99] (Pre-dose assessment)	Week 92 (Pre-dose assessment)
Week 12- Post dose	85	[72, 99] (Post dose assessment)	Week 92 (Post dose assessment)
Week 16	113	[100, 127]	Week 96
Week 20	141	[128, 155]	Week 100
Week 24	169	[156, 183]	Week 104
Week 28	197	[184, 211]	Week 108
Week 32	225	[212, 239]	Week 112
Week 36	253	[240, 267]	Week 116
Week 40	281	[268, 295]	Week 120
Week 44	309	[296, 323]	Week 124
Week 48	337	[324, 351]	Week 128
Week 52	365	[352, 379]	Week 132
Week 56	393	[380, 407]	Week 136
Week 60	421	[408, 435]	Week 140
Week 64	449	[436, 463]	Week 144
Week 68	477	[464, 491]	Week 148
Week 72	505	[492, 519]	Week 152
Week 76	533	[520, 547]	Week 156
Week 80	561	[548, 575]	Week 160
Week 84	589	[576, 603]	Week 164
Week 88	617	[604, 631]	Week 168
Week 92	645	[632, 659]	Week 172
Week 96	673	[660, 687]	Week 176
Week 100	701	[688, 715]	Week 180
Week 104	729	[716, 743]	Week 184
Week 108	757	[744, 771]	Week 188
Week 112	785	[772, 799]	Week 192
Week 116	813	[800, 827]	Week 196
Week 120	841	[828, 855]	Week 200
Week 124	869	[856, 883]	Week 204
Week 128	897	[884, 911]	Week 208
Week 132	925	[912, 939]	Week 212
Week 136	953	[940, 967]	Week 216
Week 140	981	[968, 995]	Week 220
Week 144	1009	[996, 1023]	Week 224
Week 148	1037	[1024, 1051]	Week 226
Week 152	1065	[1052, the end day of the LTE period]	Week 238

CONFIDENTIAL

The information contained herein may not be used, disclosed, or published without the written consent of Biogen MA Inc.

Table 10. Visit Windows for ADA data using Placebo controlled baseline

Analysis visit	Target visit day	Analysis visit window
Baseline	1	See baseline definition in Section 3.7.1
Week 4	29	[2, 99]
Week 24	169	[100, 253]
Week 48	337	[254, 435]
Week 76	533	[436, the end day of the placebo-controlled period ¹]
Week 80	561	[the start day of the LTE period ² , 645]
Week 104	729	[646, 771]
Week 116	813	[772, 953]
Week 156	1093	[954, 1163]
Week 176	1233	[1164, 1303]
Week 196	1373	[1304, 1471]
Week 224	1569	[1472, 1618]
Week 238	1667	≥1619

1 The end day of the placebo-controlled period is the last day before the first infusion in LTE for subjects who enter LTE, and is the last day in study for subjects who do not enter LTE.
 2 The start day of the LTE period is the day of the first infusion in the LTE period.

Table 11. Visit Windows for ADA data using LTE Baseline

Analysis visit	Target visit day	Analysis visit window	Protocol visit
Baseline	Most recent non-missing value prior to the first infusion in LTE	Most recent non-missing value prior to the first infusion in LTE	Week 80
Week 24	169	[2, 253]	Week 104
Week 48	337	[254, 435]	Week 116
Week 76	533	[436, 631]	Week 156
Week 104	729	[632, 771]	Week 176
Week 116	813	[772, 953]	Week 196
Week 156	1093	[954, 1163]	Week 224
Week 176	1233	>1163	Week 238

Day 1 is the first infusion day in LTE period

Table 12. Visit Windows for tau PET data

Analysis visit *	Target visit day	Analysis visit window
Baseline	1	Most recent non-missing pre-dose value
Week 52	364	[120, 456]
Week 78	547	[457, 727*]
Week 152	1065	[728, 1324]
Week 226	1583	>1325

* 180 days after Week 78 target date.

CONFIDENTIAL

The information contained herein may not be used, disclosed, or published without the written consent of Biogen MA Inc.

Table 13. Visit Windows for C-SSRS data using Placebo controlled baseline

Analysis visit	Target visit day	Analysis visit window
Baseline	1	Most recent non-missing pre-dose value
Week 24	169	[2, 267]
Week 52	365	[268, 456]
Week 78	547	[457, the last day of the PC period ¹]
Week 104	729	[the start day of the LTE period ² , 813]
Week 128	897	[814, 981]
Week 152	1065	[982, 1149]
Week 176	1233	[1150, 1317]
Week 200	1401	[1318, 1492]
Week 226	1583	>1492

1. The end day of the placebo-controlled period is the last day before the first infusion in LTE, and is the last day in study for subjects who do not enter LTE.
 2. The start day of the LTE period is the day of first infusion in LTE period.

Table 14. Visit Windows for C-SSRS by Visit Summaries using LTE Baseline

Analysis visit	Target visit day	Analysis visit window	Protocol visit
Baseline	Most recent non-missing value prior to the first infusion in LTE	Most recent non-missing value prior to the first infusion in LTE	Week 78
Week 24	169	[the start day of the LTE period, 253]	Week 104
Week 52	337	[254, 421]	Week 128
Week 78	505	[422, 589]	Week 152
Week 104	673	[590, 757]	Week 176
Week 128	841	[758, 932]	Week 200
Week 152	1023	> 932	Week 226

Day 1 is the first infusion day in LTE period

Table 15. Visit Windows for safety MRI data with placebo-controlled baseline

Analysis visit	Target visit day	Analysis visit window
Baseline	1	Most recent non-missing pre-dose value
Week 28	197	[90, 281]
Week 52	365	[282, 456]
Week 78	547	[457, the last day of the PC period ¹]
Week 104	729	[the start day of LTE period ² , 911]
Week 156	1093	[912, 1338]
Week 226	1583	≥ 1339

1. The end day of the placebo-controlled period is the last day before the first infusion in LTE, and is the last day in study for subjects who do not enter LTE.
 2. The start day of the LTE period is the day of first infusion in LTE period.

Table 16. Visit Windows for safety MRI data with LTE baseline

